The sample size for this study was based on the need for more information regarding the occurrence of AESI, both serious and non-serious, relative to the size of the current safety database. Evaluation of the sample size for the study objectives was performed based on the expected rate of AESI, both serious and non-serious, in patients with relapsed or refractory CD30+ HL or relapsed or refractory sALCL treated with brentuximab vedotin to ensure sufficient enrolment. The targeted sample size of 500 was determined to provide an adequate level of precision to achieve the first safety objective of this study through estimating the proportion of patients experiencing an individual AESI. The sample size of 500 includes the patients already being treated with brentuximab vedotin at the time of enrolment, the retrospective patients. It is assumed that approximately 15 to 20% (75 to 100 patients) of the study population will be retrospectively enrolled.

Interim and Final Analyses:

Details of the statistical analysis will be fully described in a written and approved statistical analysis plan (SAP). Frequency and incidence proportion for all reported SAEs and AESI will be reported for patients enrolled and receiving at least one dose of treatment. Incidence rates and 95% confidence interval (CI) will also be reported for selected events. Time at risk will be defined in the SAP. Analyses will be conducted on the enrolled population, including all patients exposed to brentuximab vedotin. In addition, analyses will be presented separately for patients prospectively and retrospectively enrolled to account for potential differences in the data reported, in particular the volume and nature of adverse events.

Subgroup safety analyses will be performed by indication and other characteristics of interest (e.g., by age at enrolment < 65 or ≥ 65 years, number of treatment cycles). All dose modifications including dose delays, temporary interruptions and permanent interruptions, and reported reason for change(s) will be summarised, and where possible the effect of modifications on safety will be explored.

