4.3 Exposure Definition and Measures

This is an observational study of real-world treatment practices in this patient population. This protocol does not recommend the use of any specific treatments. No study medication is provided as part of participation.

Patients will be enrolled after the patient agrees to participate and signs the informed consent form. All exposure to brentuximab vedotin (including any exposure prior to enrolment) will be collected.

As an observational study to understand safety in patients treated in the post-marketing setting, no restrictions on concomitant treatments are associated with the study. All concomitant treatments (and subsequent treatments for lymphoma during follow-up) will be carefully recorded in order to evaluate their potential influence on the outcomes of interest.

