4.5 Data Collection

4.5.1 Schedule of Recommended Recording of Essential Data

Essential data for the study are presented in the Schedule of Recommended Recording Essential Data provided in Table 1. For eligible patients who provide informed consent, data elements will be abstracted from information routinely recorded in the medical record. Follow-up data will be collected in conjunction with all routine care visits, typically occurring at approximately every three months. No study visits or examinations, laboratory tests or procedures are mandated as part of this study.

Confidential. Page 19 of 44

Table 1 Schedule of Recommended Recording of Essential Data

	Enrolmenta	On-Treatment Follow- up ^b	Post-Treatment Follow-up ^c (or study discontinuation)
Informed consent	X		
Demography	X		
Patient height & weight	X	X (weight only)	
ECOG Performance Status	X	X	
Relevant medical history & co-morbidities	X	X	
Laboratory test results (if performed as part of routine care)	X	X	
Relapsed or refractory CD30+ HL or sALCL disease and treatment history	X	X	
Brentuximab vedotin treatment details	X	X	
Concomitant medications	X	X	
Changes in treatment, including dose modifications		X	
Survival status			X
SAE and AESI recording in eCRF (Refer to section 7.2) ^d	X	X	
Both SAEs and AESI considered related to brentuximab vedotin - recording in eCRF (Refer to Section 7.2) ^d			X
Date and reason for discontinuation (if applicable)		X ^e	X ^e

^a Exposure to brentuximab vedotin may have started prior to enrolment. All brentuximab vedotin treatment and concomitant medication exposures, SAEs/AESI and relevant medical history since starting the current brentuximab vedotin regimen should be recorded at the time of enrolment.

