4.5.2 Baseline/Enrolment

The following data will be recorded, where available, at baseline for all enrolled patients:

- Demographics [date of birth, sex, race/ethnicity (where allowed by local regulations)]
- Weight, height (calculated BMI)
- ECOG performance status
- Relevant medical history, including cardiovascular (e.g., congestive heart failure, rhythm abnormalities), diabetes, pulmonary (e.g., chronic obstructive pulmonary

Confidential. Page 20 of 44

^b The On-Treatment period is defined as beginning at the time of enrolment and continuing through 30 days after the last dose of brentuximab vedotin.

^c The Post-Treatment Follow-up period is defined as beginning 31 days after the last dose of brentuximab vedotin and continuing until study discontinuation.

^d Refer to Section 7.2 for the procedures for recording and reporting SAEs and both serious and non-serious, AFSIs

^e Refer to section 4.5.4 for a listing of data to be recorded at the time of study discontinuation.

disease), hepatic, renal, other malignancies, neurologic (e.g., neuropathies), autoimmune disease, infectious disease (e.g., HIV, Epstein Barr virus), abnormal blood counts (cytopenias and growth factor exposure), thyroid dysfunction

- Relevant laboratory testing [e.g., haematology, lactate dehydrogenase (LDH), CD30 expression %], if performed as part of routine care
- CD30+ HL or sALCL disease and treatment history
 - o Disease type (CD30+ HL or sALCL)
 - o Date of initial diagnosis
 - Diagnostic testing performed
 - o Disease stage
 - Presence of lymphoma-related symptoms (B symptoms)
 - o Extent of disease determined by both physical examination and imaging
 - o ALK status (positive, negative, unknown) (sALCL patients only)
 - o ALCL variant: common, small cell, lymphohistiocytic, sarcomatoid, other, unknown (sALCL patients only)
 - o HL subtype: nodular sclerosing, mixed cellularity, lymphocyte-rich, lymphocyte depleted, unspecified/unknown
 - o Previous treatment
 - Previous lines of therapy, with number of cycles
 - Autologous stem cell transplant or allogeneic stem cell transplant
 - Radiation therapy
- Brentuximab vedotin treatment, including dose and treatment date for current regimen and any changes in treatment dose prior to enrolment
- Occurrence of SAEs and both serious and non-serious AESI (per Section 7.2 Procedures for Recording and Reporting SAEs and AESI) since start of current treatment regimen of brentuximab vedotin
- Concomitant medications

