5.2.2 Planned analyses

5.2.2.1 Primary analyses

Serious Adverse Events (SAEs) and Adverse Events of Special Interest (AESI)

SAEs and AESI (including both serious and non-serious AESI) will be summarized by MedDRA system organ class (SOC) and preferred term (PT). Frequency and incidence proportion for all SAEs and AESI (as defined in Section 4.4.1) will be reported for patients who received at least one dose of brentuximab vedotin while on study.

The incidence rate and the associated 95% CI will be reported for SAEs and AESI.

Time at risk of SAEs and AESI will correspond to current/recent treatment with brentuximab vedotin. Current/recent treatment will be defined as time between the dates of first and last dose plus 30 days. All other follow-up time accrued for the patient will be considered occurring during past treatment with brentuximab vedotin; events reported during the past treatment period will be presented separately.

In addition, select events will be displayed by timing in relation to treatment start (e.g., by number of completed cycles) or time-to-event analysis may be carried out using Kaplan-Meier plots for the occurrence of the first reported occurrence of the adverse event, as appropriate for the event.

Identification and Description of Risk Factors for Peripheral Neuropathy

In addition, multivariable adjusted analysis will be performed to identify and describe risk factors for peripheral neuropathy (e.g., BMI, previous history of neuropathy, known toxic exposures) in the cohort. Risk factors for the first occurrence of new onset or worsening of peripheral neuropathy will be explored using a multivariable adjusted Cox regression model. Model assumptions concerning proportionality will be evaluated graphically in the usual manner. The inclusion of specific risk factors will be described in the SAP. A preliminary univariate analysis of the association of variables of interest with the outcome measure will be

Confidential. Page 24 of 44

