7.2.1 Events to be recorded in the eCRF

All SAEs and both serious and non-serious AESI will be recorded in the eCRF, from the patient's first dose of brentuximab vedotin through 30 days after the patient's last dose of brentuximab vedotin. For retrospectively enrolled patients, this includes any SAEs or both serious and non-serious AESI identified in the medical record which occurred prior to study enrolment but after initiating the current regimen of brentuximab vedotin. From 31 days after the patient's last dose of brentuximab vedotin, only SAEs and both serious and non-serious AESI considered related to brentuximab vedotin will be recorded in the eCRF (see Table 3).

Documentation regarding an SAE or both serious and non-serious AESI, observed by the investigator or reported by the patient upon indirect questioning, should be made as to the

Confidential. Page 31 of 44

nature, date of onset, end date, severity, relationship to brentuximab vedotin, action(s) taken, and outcome.

If any of the same SAE or both serious and non-serious AESI, occur on several occasions in the same patient, then the event in question must be documented and assessed each time.

7.2.2 Events to be reported to Millennium Pharmacovigilance & Risk Management (PV&RM) or designee (in addition to being recorded in the eCRF)

All SAEs (regardless of relationship to brentuximab vedotin) and both serious and non-serious AESI considered related to brentuximab vedotin, occurring from the patient's first dose of brentuximab vedotin in the current regimen through 30 days after the patient's last dose of brentuximab vedotin, must also be reported to Millennium PV&RM or designee by faxing a completed SAE Form within one business day after becoming aware of the event (see Table 3). For retrospectively enrolled patients, this includes any SAEs (regardless of relationship to brentuximab vedotin) or AESI, both serious and non-serious, considered related to brentuximab vedotin identified in the medical record which occurred prior to study enrolment but after initiating the current regimen of brentuximab vedotin.

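### For patients who stop for more than 30 days and restart, time at risk counts the off-drug gap as current treatment; the safety set is also worded in three ways

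*Protocol*

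**What the plan says.** **Denominator.** Section 5.2.2.1 sets time at risk as a single span: "Current/recent treatment will be defined as time between the dates of first and last dose plus 30 days". Everything later is past treatment, and "events reported during the past treatment period will be presented separately". The section has no rule for a break in dosing between the first and last dose.

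**Events.** Section 7.2 and Table 3 collect all SAEs and AESI, related or not, from first dose to 30 days after last dose. From day 31, section 7.2.1 narrows this: "only SAEs and both serious and non-serious AESI considered related to brentuximab vedotin will be recorded in the eCRF". Section 4.5.4 (post-treatment follow-up) likewise lists only related events.

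**Start of collection.** Section 4.3 says "All exposure to brentuximab vedotin (including any exposure prior to enrolment) will be collected". Table 1, footnote a, is narrower: treatment and events "since starting the current brentuximab vedotin regimen should be recorded at the time of enrolment". Sections 4.5.2 and 7.2.1 also refer to the current regimen.

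**Population.** Section 5.2.1 analyses everyone enrolled. The synopsis reports frequency and incidence proportion "for patients enrolled and receiving at least one dose of treatment". Section 5.2.2.1 reports them for "patients who received at least one dose of brentuximab vedotin while on study".

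**The concern.** A rate is interpretable only if events are counted over the same time that fills the denominator. Section 5.2.2.1 depends on the last dose, which is known only in hindsight. Recording at the site happens as time passes. When a patient has been off drug for 31 days, the site moves to related-only recording because it cannot know that treatment will resume. If dosing restarts, the analysis rule turns the whole gap into current/recent time, although unrelated SAEs and AESI in it may never have been entered.

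The situation is foreseeable. Sections 4.4.3 and 5.2.2.1 plan to summarise temporary interruptions, and section 4.5.3 expects transplants and new lines of therapy during follow-up. Section 7.1 defines AESI regardless of relationship to treatment, so related-only recording loses part of the outcome.

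The rates stand under primary analyses. Wording that can drop retrospective patients from the safety set also affects the proportions, on which the sample size rests.

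**Working it through.** **1. The plan's own figure.** The only computed figures are the intervals in Table 2, for proportions with N = 500. They reproduce with a continuity-corrected normal approximation. For 25 events: 0.05 ± (1.96 × √(0.05 × 0.95/500) + 1/1000) = 0.05 ± 0.0201, or 2.99% to 7.01%, against 3.0% to 7.0% in the table. The zero-event row matches the exact upper limit of 0.74%. Person-time does not enter these, so Table 2 is unaffected. The protocol states no expected rate or person-time.

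**2. The two windows side by side.**

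| Period | Time at risk (5.2.2.1) | Events recorded (4.5.4, 7.2) |
|---|---|---|
| One course: first dose to last dose + 30 days | Yes | All |
| One course: from day 31 after last dose | No, past treatment | Related only |
| Restart: first 30 days of the gap | Yes | All |
| Restart: day 31 of the gap to the restart | Yes, once dosing resumes | Related only, if the rule is applied as time passes |
| Restart: second course + 30 days | Yes | All |

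The mismatch is confined to the fourth row.

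**3. Size in one patient (assumed history).** Take 24 weeks on drug, 52 off and 18 on again; 30 days is 30/7 = 4.29 weeks.
- Single span: 24 + 52 + 18 + 4.29 = 98.3 weeks.
- Episodes: (24 + 4.29) + (18 + 4.29) = 50.6 weeks.
- Ratio: 50.6/98.3 = 0.51. With no event recorded in the late gap, this patient's rate is about halved.

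**4. Size in the cohort (assumed shares and gaps).** Let B be properly observed weeks per patient, f the share of patients who restart, and G the gap beyond its 30-day tail. With no events recorded in G, the reported rate is the correct rate times B/(B + f × G).
- B = 27 + 4.29 = 31.29 weeks, using the Hodgkin lymphoma phase 2 median from section 1 as if it were a mean.
- A 52-week gap gives G = 52 − 4.29 = 47.71. A 13-week gap gives G = 8.71.
- The protocol gives neither f nor the gap length.

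| f | 13-week gap | 52-week gap |
|---|---|---|
| 0% | 1.00 | 1.00 |
| 5% | 31.29/31.72 = 0.986 | 31.29/33.67 = 0.929 |
| 10% | 31.29/32.16 = 0.973 | 31.29/36.06 = 0.868 |
| 15% | 31.29/32.59 = 0.960 | 31.29/38.44 = 0.814 |

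The last column is a shortfall of about 7%, 13% and 19%. With the sALCL median of 20 weeks (B = 24.29), the 52-week factors are 0.911, 0.836 and 0.772. Any related event recorded in the gap enters the numerator and shrinks the shortfall, so for a given share and gap these are upper bounds.

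**5. Safety set.** Retrospective patients are an assumed 75 to 100 of 500 (section 5.1). One who is on treatment at consent but gets no further dose has events collected under section 7.2.1, yet can fall outside "patients who received at least one dose of brentuximab vedotin while on study". The number of such patients is not given.

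**The case against.** **Most patients are unaffected.** This stands. For a single continuous course the windows coincide. Related-only recording after the final dose does no harm, because that time is already outside the denominator. A reader might infer that every rate is diluted; the documents do not support that.

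**Earlier regimens do not enter the denominator.** This largely stands. A reader might infer from "All exposure to brentuximab vedotin (including any exposure prior to enrolment) will be collected" that person-time from earlier courses is counted while their events are not. But section 7.2.2 words Table 3's window as starting with the first dose in the current regimen, and footnote a and section 4.5.2 start exposure and events together. Footnote b does start a period at enrolment ("The On-Treatment period is defined as beginning at the time of enrolment and continuing through 30 days after the last dose"), but it describes the recording schedule, not time at risk. What remains is loose wording in sections 4.3 and 5.2.2.1. Nor are earlier courses lost: the baseline data already include previous lines of therapy with cycle counts.

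**Read literally, the related-only rule starts after the final dose, so full collection applies in the gap.** This stands only in hindsight. No section tells sites to go back over a gap when treatment resumes; section 4.5.3 asks only for events since the previous follow-up. Even with full capture, off-drug time would be labelled current treatment.

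**The synopsis leaves time at risk to the statistical analysis plan.** It does, but section 5.2.2.1 then states a definition. A later plan could remove gap time from the denominator; it could not recover events never entered.

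**The population wording is a minor matter.** Partly right. Patients never dosed add no person-time, and both places that define the incidence proportion require a dose. The on-study condition still conflicts with the collection rule for retrospective patients.

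**Conclusion.** The point holds for a limited group. In patients who stop for more than 30 days and restart under observation, the single-span definition counts off-drug time with incomplete event recording as time at risk, and their rates are understated. The number of such patients is unknown. The 7%, 13% and 19% shortfalls assume a 52-week gap with no recorded events in 5%, 10% or 15% of patients and a base of 31.3 weeks. They illustrate an upper bound under those inputs and are not estimates; with no such patients the effect is zero. It also rests on sites applying the day-31 rule in real time.

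The three population wordings conflict on the page and need no such assumption. Overall importance is moderate: the text should be corrected, but the proportions, Table 2 and the sample size do not depend on person-time.

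**What to change.** - In section 5.2.2.1, define time at risk as the union of on-drug episodes. Each runs from its first dose to its last dose plus 30 days, and a new episode begins when the off-drug gap outlasts that 30-day tail. Start at the first dose of the current regimen, and truncate at death, withdrawal or data cut.
- Classify gap time beyond the tail, and events in it, as past treatment, so that numerator and denominator leave the rate together.
- Reconcile section 4.3 with Table 1 footnote a and sections 4.5.2 and 7.2.1, so that exposure and events share one stated start.
- Use one safety set in the synopsis and sections 5.2.1 and 5.2.2.1: all enrolled patients with at least one dose in the current regimen, before or after consent.

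The cost is wording in those sections and minor episode programming from dose dates already collected. A new baseline field for earlier courses would be largely redundant, given the cycle counts by previous line of therapy.

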In SG035-0003, a phase 2, single-arm, open-label study in patients with relapsed or refractory HL postASCT, and in SG035-0004, a phase 2 trial conducted in patients with relapsed or refractory sALCL, brentuximab vedotin was administered at a dose of 1.8 mg/kg every 3 weeks. One hundred two patients with relapsed and refractory HL and 58 patients with relapsed and refractory sALCL were exposed for a median duration of approximately 27 weeks (9 cycles) and 20 weeks (6 cycles), respectively. The primary endpoint of both studies was overall response rate. Treatment-emergent AEs occurring in $\geq 20\%$ of patients in phase 2 were peripheral sensory neuropathy (44%), fatigue (42%), nausea (41%), diarrhoea (34%), pyrexia (31%), upper respiratory tract infection (28%), neutropenia (21%) and vomiting (20%). These events were primarily mild to moderate in severity and reversible. Approximately half of patients had treatment-emergent peripheral neuropathy, predominantly sensory neuropathy, with an onset and severity pattern consistent with a cumulative effect of exposure. Dose delay and subsequent reduction to 1.2 mg/kg was generally effective in managing peripheral neuropathy. Moderate or severe neutropenia occurred in 13% and 7% of patients, respectively; these events were typically of short duration and well managed by brief dose delays with growth factor support in some cases. Infusion-related reactions occurred in approximately 10% of patients and were typically managed by dose delay or reduction. The clinical laboratory parameters for which the most patients had new or worsening findings were low neutrophils, low lymphocytes, low platelets, low leukocytes and elevated glucose [Younes 2012].

Most patients in the two phase 2 studies were between the ages of 18 and 65 years; as a result, there are limited data available regarding the use of brentuximab vedotin in elderly patients. In addition, the maximum number of cycles administered in the pivotal phase 2 studies was 16 and it is unknown whether there is any change in the safety profile of brentuximab vedotin

Confidential. Page 14 of 44

with longer term use or with the implementation of the recommended dose reductions in the presence of specific toxicities.

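### Optional Kaplan-Meier plots of first adverse events overstate on-treatment risk if read as absolute risk; use cumulative incidence or label them

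*Protocol*

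**What the plan says.** Objective 1 (Protocol Section 3) is to evaluate how often SAEs and AESI occur in patients actively treated in routine practice. Section 5.2.2.1 commits to two summaries: "Frequency and incidence proportion for all SAEs and AESI (as defined in Section 4.4.1) will be reported for patients who received at least one dose" while on study, and "The incidence rate and the associated 95% CI will be reported for SAEs and AESI".

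The same section sets the time at risk: "Current/recent treatment will be defined as time between the dates of first and last dose plus 30 days". Beyond that, "events reported during the past treatment period will be presented separately". A further display is then offered for selected events, either by timing (for example completed cycles) or as a curve: "time-to-event analysis may be carried out using Kaplan-Meier plots for the occurrence of the first reported occurrence of the adverse event", where that suits the event. No competing-risk estimator is named, and no rule says how death or the end of the window enters the curve.

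Two other provisions bear on this. Section 7.2.1 and Table 3 restrict recording from day 31 after the last dose to events judged related to brentuximab vedotin. The Synopsis ends follow-up at death, withdrawal of consent, loss to follow-up or study closure.

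**The concern.** A Kaplan-Meier curve knows only events and censored times. A curve of first AESI regardless of causality cannot run past the window, because unrelated events are no longer recorded there. A patient who dies, or reaches the end of the window without the event, therefore leaves the curve as censored. One minus Kaplan-Meier then estimates the risk in a cohort where nobody dies or stops, provided those who leave would have had the same hazard as those who stay. Objective 1 asks for something else: how often the event occurs in patients as they are treated.

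The difference is largest late in the curve. In phase 2, HL and sALCL patients were "exposed for a median duration of approximately 27 weeks (9 cycles) and 20 weeks (6 cycles), respectively", with a maximum of 16 cycles, so about half had left treatment well before the longest exposures. An unlabelled curve beside the incidence proportion for the same event would give a higher figure with no explanation, and a reader could take it as the risk to quote.

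**Working it through.** The protocol gives no Kaplan-Meier or competing-risk figure to reproduce. Table 2 concerns the incidence proportion and is not touched. What follows is an illustration under assumptions.

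**Inputs from the protocol (Section 1, phase 2 studies).** Median exposure 27 weeks (HL) and 20 weeks (sALCL); peripheral neuropathy in about half of patients, sensory neuropathy in 44%; at most 16 cycles, given every 3 weeks, so 16 × 3 = 48 weeks. Section 5.2.2.1 adds 30 days: T = 48 + 30/7 = 52.3 weeks.

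**Assumed, not in the protocol.** Constant hazards; 2% to 20% of patients dying in the window.

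**Formulas.** With event hazard a and competing hazard c:
- cumulative incidence: CIF(T) = a/(a+c) × [1 − exp(−(a+c)T)]
- one minus Kaplan-Meier: 1 − exp(−aT)

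In steps 1 and 2, a is solved so that CIF(T) equals the stated true risk.

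**Step 1: death as the only competing event.** c = −ln(1−d)/T, where d is the proportion dying.

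Worked case, d = 10%, true risk 50%: cT = 0.105 and the solution is aT = 0.741. Check: 0.741/0.846 × (1 − e^−0.846) = 0.876 × 0.571 = 0.500. Then 1 − e^−0.741 = 52.3%.

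| Deaths in window | Excess at true 50% | Excess at true 10% |
|---|---|---|
| 2% | 0.45 points | 0.10 points |
| 5% | 1.14 points | 0.25 points |
| 10% | 2.34 points | 0.53 points |
| 20% | 4.98 points | 1.13 points |

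**Step 2: event-free end of the window as the competing event.** c = ln 2/(median exposure + 30/7), that is ln 2/31.3 or ln 2/24.3 per week.

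Worked case, 27-week median, true risk 50%: cT = 1.158 and aT = 1.377. Check: 1.377/2.535 × (1 − e^−2.535) = 0.543 × 0.921 = 0.500. Then 1 − e^−1.377 = 74.8%.

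| Median exposure | Reading at true 50% | Reading at true 10% |
|---|---|---|
| 27 weeks | 74.8% | 16.6% |
| 20 weeks | 80.5% | 18.8% |

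**Step 3: a second parameterisation, read at 48 weeks.** Here the hazards are set so that 50% (or 44%) of patients eventually have neuropathy before leaving.
- 27-week median, 50%: a = c = ln 2/27 = 0.0257. 1 − e^(−0.0257×48) = 71%, against 0.5 × (1 − e^(−0.0513×48)) = 46%.
- Same median, 44%: 62% against 39%.
- 30 days added, 50%: 65% against 44% (27-week median) and 75% against 47% (20-week median).

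For neuropathy the gap exceeds 20 points in every scenario of steps 2 and 3. Almost all of it comes from counting treatment end as competing; step 1 shows how little death alone contributes.

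**The case against.** The strongest reply is that the protocol states no censoring rule, leaves analysis detail to an SAP that is not shown, and makes the plot optional and supplementary. Objective 1 is answered by the incidence proportion and incidence rate, the sample size rests on the proportion, and no test depends on the curve. All of this stands, and it is why the point is minor. It does not remove the point: given the recording rules, further SAP detail cannot make an ordinary Kaplan-Meier curve of all first AESI handle these exits as anything but censoring. The curve may also matter at the interim analysis. At about 2.5 years, with enrolment running for about 3, some patients will still be on treatment, and a crude proportion understates their eventual risk. A time-to-event estimate is the natural remedy, and Aalen-Johansen handles open windows and competing exits together.

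A second reply is that risk under continued treatment is a legitimate target, since the protocol asks about exposure beyond 16 cycles. That also stands. How to treat the end of treatment is a choice of estimand, so a clear label is enough and Kaplan-Meier need not be excluded.

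A reader might also infer that censoring is informative for neuropathy because neuropathy leads to stopping. For a first-event curve this fails: a patient who stops for neuropathy has already had the event. The worry could apply to other AESI, since 30% of patients in one phase 1 study discontinued because of adverse events, but the documents do not show that such stopping predicts those events.

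**Conclusion.** The point holds as a minor one, a cheap improvement. Read as absolute on-treatment risk, one minus Kaplan-Meier over the protocol's window is too high. For death alone the excess is about 0.5 to 5 points at a true 50% and 0.1 to 1.1 points at a true 10%, if 2% to 20% die in the window. If event-free treatment end also counts as competing, it is potentially 20 points or more for neuropathy.

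The direction is firm and the size is not. The protocol gives no death rate in the window, the exposure medians come from phase 2 rather than routine care, and constant hazards are a simplification: Section 1 describes neuropathy as following a cumulative effect of exposure.

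Two stronger readings are not supported. The documents do not show that the main safety estimates are biased; the incidence proportions and rates do not depend on the curve. Nor is a gap of 20 points or more an established error: it arises only if the curve is drawn, left unlabelled and read as the share of treated patients affected.

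**What to change.** Add to Section 5.2.2.1, with the detail in the SAP:

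- Where a time-to-event curve is presented as absolute risk, use the Aalen-Johansen cumulative incidence of the first event with death as a competing event. For on-treatment risk, add event-free end of the window (last dose plus 30 days) as a further competing event. Censor only at data cut, withdrawal or loss to follow-up.
- Label any Kaplan-Meier curve that censors at treatment end as risk conditional on continued treatment.
- Keep the Cox model for neuropathy risk factors. With competing exits censored it estimates cause-specific hazards, which suit that question.

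The cost is a sentence or two, slightly more analysis with standard methods, and care in labelling. No new data are needed.
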